15.2 Repeated or Unscheduled Assessments of Safety Parameters

If a patient has repeated assessments before the start of the study treatment, the results from the last non-missing assessment made prior to the start of the study treatment will be used as baseline. If end-of-study assessments are repeated or if unscheduled visits occur, the last non-missing postbaseline assessment will be used as the end-of-study assessment for generating summary statistics. However, all postbaseline assessments will be used for PCS value determinations, and all assessments will be presented in the data listings.

15.3 Missing Severity Assessment for Adverse Events

If severity is missing for an AE that started before the date of the study treatment, an intensity of mild will be assigned. If severity is missing for an AE that started on or after the date of the study treatment, an intensity of severe will be assigned. The imputed values for severity assessment will be used for the incidence summary; the values will be shown as missing in the data listings.

15.4 Missing Causal Relationship to Study Drug for Adverse Events

If the causal relationship to the study treatment is missing for an AE that started on or after the date of the study treatment, a causality of yes will be assigned. The imputed values for causal relationship to study treatment will be used for the incidence summary; the values will be shown as missing in the data listings.

15.5 Missing Date Information for Adverse Events

The following imputation rules only apply to cases in which the start date for AEs is incomplete (i.e., partly missing).

Missing month and day

- If the year of the incomplete start date is the same as the year of the study treatment, the month and day of the study treatment will be assigned to the missing fields
- If the year of the incomplete start date is before the year of the study treatment, *December 31* will be assigned to the missing fields
- If the year of the incomplete start date is after the year of the study treatment, *January 1* will be assigned to the missing fields

Missing month only

• If only the month is missing, the day will be treated as missing and both the month and the day will be replaced according to the above procedure

Missing day only

- If the month and year of the incomplete start date are the same as the month and year of the study treatment, the day of the study treatment will be assigned to the missing day
- If either the year of the incomplete start date is before the year of the date of the study treatment or if both years are the same, but the month of the incomplete start date is before the month of the date of the study treatment, the last day of the month will be assigned to the missing day

• If either the year of the incomplete start date is after the year of the date of the study treatment or if both years are the same, but the month of the incomplete start date is after the month of the date of the study treatment, the first day of the month will be assigned to the missing day

If the stop date is complete and the imputed start date as above is after the stop date, the start date will be imputed by the stop date.

If the start date is completely missing and the stop date is complete, the following algorithm will be used to impute the start date:

- If the stop date is after the date of the study treatment, the date of the study treatment will be assigned to the missing start date
- If the stop date is before the date of the study treatment, the stop date will be assigned to the missing start date

15.6 Missing Date Information for Prior or Concomitant Medications

For prior or concomitant medications, including rescue medications, incomplete (i.e., partly missing) start dates and/or stop dates will be imputed. When the start date and the stop date are both incomplete for a patient, the start date will be imputed first.

15.6.1 Incomplete Start Date

The following rules will be applied to impute the missing numeric fields for an incomplete prior or concomitant medication start date. If the stop date is complete (or imputed) and the imputed start date is after the stop date, the start date will be imputed using the stop date.

Missing month and day

- If the year of the incomplete start date is the same as the year of the study treatment, the month and day of the study treatment will be assigned to the missing fields
- If the year of the incomplete start date is before the year of the study treatment, *December 31* will be assigned to the missing fields
- If the year of the incomplete start date is after the year of the study treatment, *January 1* will be assigned to the missing fields

Missing month only

• If only the month is missing, the day will be treated as missing and both the month and the day will be replaced according to the above procedure

Missing day only

- If the month and year of the incomplete start date are the same as the month and year of the study treatment, the day of the study treatment will be assigned to the missing day
- If either the year of the incomplete start date is before the year of the date of the study treatment or if both years are the same, but the month of the incomplete start date is before the month of the date of the study treatment, the last day of the month will be assigned to the missing day.
- If either the year of the incomplete start date is after the year of the date of the study treatment or if both years are the same, but the month of the incomplete start date is after the month of the date of the study treatment, the first day of the month will be assigned to the missing day

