8.0 Demographics and Other Baseline Characteristics

Demographic parameters (age; age group; race; ethnicity; sex), baseline characteristics (weight; height; and body mass index, calculated as weight [kg]/(height [m])²), waist circumference (m), and other disease characteristics (type of surgery and number of grafts) will be summarized descriptively by treatment group for the safety population. Continuous variables will be summarized by number of participants and mean, SD, first quartile (Q1), median, minimum, third quartile (Q3), and maximum values. Categorical variables will be summarized by number and percentage of participants.

Medical history data will be coded using the Medical Dictionary for Regulatory Activities (MedDRA). The number and percentage of participants with medical history ongoing at screening will be summarized by system organ class, preferred term, and treatment group for the safety population. Data for medical history that is not ongoing at screening will be summarized and presented in a similar manner. An overall total will be provided for the study as well as by treatment group.

Prior medication is defined as any medication taken before the study treatment. Concomitant medication is defined as any medication taken on or after the day of study treatment.

Both prior and concomitant medications will be coded using the Anatomical-Therapeutic-Chemical classification text from World Health Organization (WHO) Drug Dictionary. The use of prior and concomitant medications will be summarized by the number and percentage of subjects in each treatment group for the safety population. If a participant took a specific medication multiple times or took multiple medications within a specific therapeutic class, that participant would be counted only once for the coded drug name or therapeutic class.

In addition to summarizing all medications as discussed above, a separate tabulation will also be provided for the following medications of interest:

- The following antiarrhythmics: quinidine, procainamide, disopyramide, mexiletine, flecainide, propafenone, amiodarone (including amiodarone hydrochloride, amiodarone hydrochloride w/ glucose and amiodarone;glucose), dronedarone, dofetilide, sotalol (including sotalol hydrochloride), and ibutilide.
- The following anticoagulants: warfarin (including warfarin sodium), dabigatran, apixaban, rivaroxaban, and edoxaban (including edoxaban tosilate).

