The following five binary (yes/no) variables will be used to analyze the need for pharmacologic and/or procedural intervention due to AF during the first 30 days post-surgery:

- 1. at least one pharmacologic intervention (i.e., anticoagulation or antiarrhythmic drugs)?
- 2. at least one anticoagulation pharmacologic intervention?
- 3. at least one antiarrhythmic pharmacologic intervention?
- 4. at least one procedural intervention (see list in Section 8.0)?
- 5. at least one pharmacologic or procedural intervention?

In addition, time to event variables will also be created for each of the corresponding 5 variables above. The time to the first event will be used for analysis. All these variables will be analyzed using the same methods for similar variables in Sections 10.1 and 10.2.

The need for pharmacologic and/or procedural intervention due to AF from Day 31 to Day 360 post-surgery will be analyzed in a similar fashion. Participants with no events who exit the study prior to Day 360 will be censored at their respective study exit day minus 30 days, while participants with no events who exit the study on or beyond day 360 will be censored at day 330 (360 - 30 = 330). Pharmacologic and/or procedural interventions due to AF with onset dates prior to day 31 that are ongoing at day 31 will count as events for these endpoints, with a time-to-event equal to zero.

Descriptive statistics will be presented by treatment group for each of the following:

- time to POAF resolution from first dose of prescription of pharmacologic intervention
- time to POAF resolution from first procedural intervention
- types of pharmacologic interventions used due to POAF

- will be further categorized by "medication of interest" (antiarrhythmics versus anticoagulants) as defined in Section 8.0 above.
- yes/no: Beta blocking agent (ATC code: C07A) withdrawn within 3 days post-surgery and no replacement (no new beta blocker prescription) within 7 days post-surgery

Other Efficacy Variables

- Percentage of participants with clinically important tachycardia in AF (defined as heart rate ≥ 100 bpm for at least 2 minutes) within 30 days post-surgery
- Percentage of participants with any occurrence of AF as defined in the primary and secondary endpoints during the first 7 days following Day 60, Day 90, Day 180, Day 270, and Day 360 visits

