15.6.2 Incomplete Stop Date

The following rules will be applied to impute the missing numeric fields for an incomplete prior or concomitant medication stop date. If the date of the study exit is missing, the last available study visit date will be used as the study exit date.

Missing month and day

- If the year of the incomplete stop date is the same as the year of the study exit, the month and day of the study exit will be assigned to the missing fields
- If the year of the incomplete stop date is before the year of the study exit, *December 31* will be assigned to the missing fields
- If the year of the incomplete stop date is after the year of the study exit, *January 1* will be assigned to the missing fields

Missing month only

• If only the month is missing, the day will be treated as missing and both the month and the day will be replaced according to the above procedure

Missing day only

- If the month and year of the incomplete stop date are the same as the month and year of the study exit, the day of the study exit will be assigned to the missing day
- If either the year of the incomplete stop date is before the year of the date of the study exit or if both years are the same, but the month of the incomplete stop date is before the month of the date of the study exit, the last day of the month will be assigned to the missing day

• If either the year of the incomplete stop date is after the year of the date of the study exit or if both years are the same, but the month of the incomplete stop date is after the month of the date of the study exit, the first day of the month will be assigned to the missing day

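### SAP 15.6 pushes most partial drug stop dates late and some partial starts to the day of surgery, and SAP 10.3 and 6.4 use these dates as outcomes, so short AF-drug courses can become false late events.

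*SAP*

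**What the plan says.** SAP 15.6 puts one set of rules over every drug record: "For prior or concomitant medications, including rescue medications, incomplete (i.e., partly missing) start dates and/or stop dates will be imputed".

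**Stop dates (15.6.2).** If the known parts match the year, or the month and year, of study exit, the exit date is used. If they fall before exit, the date becomes 31 December, or "the last day of the month will be assigned to the missing day". Only if they fall after exit does the date go to the first day of the year or month.

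**Start dates (15.6.1).** Surgery and study treatment fall on the same day. Surgery is assigned in two cases:
- only the year is known and it is "the same as the year of the study treatment, the month and day of the study treatment will be assigned to the missing fields";
- only the day is missing, and the month and year are "the same as the month and year of the study treatment, the day of the study treatment will be assigned to the missing day".

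Earlier dates stay pre-operative. With only the year known, if that year "is before the year of the study treatment, *December 31* will be assigned to the missing fields"; with the day missing, if the month is "before the month of the date of the study treatment, the last day of the month will be assigned to the missing day". An imputed start later than the stop is pulled back to the stop.

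**Where the dates are used.**
- SAP 8.0: "Prior medication is defined as any medication taken before the study treatment".
- SAP 10.3: five yes/no variables for AF-related drug or procedural intervention in the first 30 days. "In addition, time to event variables will also be created for each of the corresponding 5 variables above". For Days 31-360, an intervention begun earlier and still running at Day 31 is an event with time zero. AF-drug use also enters actionable AF, the variables on being AF-free and off drug, and the win ratio.
- SAP 6.4: an analysis set defined by beta-blocker withdrawal within 3 days and no replacement within 7. SAP 10.1 uses this set for a supplementary analysis of the primary variable.

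**The concern.** Rules of this kind suit a prior/concomitant table, where it is cautious to call a doubtful drug concomitant. Here the same dates also decide whether an outcome occurred and when, and nothing in the SAP limits 15.6 to the tables or overrides it for efficacy.

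The stop-date rule leans late and meets a carry-over rule that turns anything running at Day 31 into a late event. A few days of AF treatment in hospital can then be analysed as need for treatment after Day 30. The same lean takes true early withdrawals out of the beta-blocker set.

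The start-date rule can give an AF drug taken before surgery a Day 1 start. The drug then leaves the prior-medication table and may enter the 30-day variables at time zero. A drug begun months later with only the year known can also be moved to Day 1. At stake is the reading of the AF-drug variables and the win ratio.

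**Working it through.** The plan gives no figure to reproduce. The check applies 15.6.1 and 15.6.2 literally to a surgery on each of the 365 days of a year. Assumptions: surgery evenly spread, exit at Day 367, Day 1 = treatment (as in SAP Table 15-1). Every share is conditional on the date being partial.

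**1. Stop date, day missing.** A true stop on day *j* of a month with *m* days is moved to day *m*, which adds *m* − *j* days. A true stop on Day *D* reaches Day 31 if *m* − *j* ≥ 31 − *D*. That holds for *m* − 31 + *D* days of each month. Summed over 12 months: 365 − 372 + 12*D* = 12*D* − 7, so the share is (12*D* − 7)/365.

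| True stop | Share imputed to Day 31 or later |
|---|---|
| Day 6 | 65/365 = 18% |
| Day 10 | 113/365 = 31% |
| Day 14 | 161/365 = 44% |
| Day 20 | 233/365 = 64% |
| Days 5-30, evenly (mean *D* = 17.5) | 203/365 = 55.6% |

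The mean number of days added is 5373/365 = 14.7, where 5373 is the sum of *m*(*m* − 1)/2 over the months. SAP 10.0 counts post-surgery time from ICU admission; each day's shift in the threshold changes a share by 12/365 = 3.3 points.

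Example: surgery 25 January, true stop 3 February (Day 10). The imputed stop is 28 February = Day 35, a Day 31-360 event at time zero.

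**2. Stop date, month and day missing.** The imputed stop falls short of Day 31 only when 31 December lies between Day *D* and Day 30, which is 31 − *D* surgery dates. The share imputed late is 1 − (31 − *D*)/365: 94% for Day 10, and 1 − 13.5/365 = 96.3% over Days 5-30.

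**3. Beta-blocker set (SAP 6.4), true stop on Day 2, day missing.** The imputed stop is Day 3 or earlier only if the true stop is one of the last two days of a month: 24/365 = 7%. If three days post-surgery is read as Day 4, it is the last three days: 36/365 = 10%.

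**4. Pre-operative start, drug ongoing at surgery, *L* days before.**
- Day missing: moved to surgery only if the start is in the surgery month, giving 281/365 = 77% at 7 days, 197/365 = 54% at 14, 7/365 = 2% at 30 and 0% at 90. Averaged over *L* = 1 to 365: 5373/365² = 4%.
- Month and day missing: (365 − *L*)/365, giving 75% at 90 days, 51% at 180 and 0% at 365. The average over *L* = 1 to 365 is 182/365 = 50%.
- With a complete stop date before surgery, none is moved, because the start is pulled back to the stop.

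Example: surgery 20 March, true start 10 January. Day missing gives 31 January, still pre-operative. Month and day missing gives 20 March, the day of surgery.

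**5. Later start, true Day *D*, month and day missing.** Moved to Day 1 in (366 − *D*)/365. Over Days 31-360 (mean 195.5) this is 170.5/365 = 47%.

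**The case against.** The case against is substantial, and most of it limits size.

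- **Most partial starts are not moved to surgery.** A reader might infer that every incomplete start becomes the surgery date. 15.6.1 does not say so: earlier months and years stay pre-operative, and a complete pre-operative stop protects the start. This stands.
- **Antiarrhythmics are largely protected.** The protocol excludes Class I and III drugs unless washout is documented (Sections 5.2 and 6.5.1), so a pre-operative stop should be known. The exposed group is mainly anticoagulants in participants with paroxysmal AF, whom inclusion criterion 6.01 allows. This stands.
- **Dates alone do not make an event.** SAP 10.3 counts interventions due to AF, and protocol Table 8-4 records whether a drug was prescribed for POAF, a test that a chronic drug fails. This stands in part. The SAP wording is wider than POAF, and it never says whether an AF drug already in use at surgery counts. That gap exists with complete dates too.
- **Partial dates may be few.** Protocol 6.5.2 requires start and end dates, 6.5.3 asks for date and time of administration, and medication is reviewed at each visit. A year-only stop for an in-hospital course is implausible. So the day-missing figures matter more than the 96%, and none of the shares is an effect size.
- **Bias is not simply toward zero.** A reader might infer general dilution. If a share *f* of non-events in every arm became false events, the risk difference would be multiplied by 1 − *f*. That can describe start-date errors unrelated to arm. False Day 31 events arise only in participants treated early. If the active arms need less early treatment, such events are commoner on placebo and carry the early difference into the late variable.
- **Reach is limited.** A reader might infer that the primary result is at risk. The mITT primary analysis and the episode-duration endpoints come from the ECG patch and use no drug dates. No stopping or arm-dropping rests on the affected variables.

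These points do not remove the stop-date mechanism, which needs only one missing day.

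**Conclusion.** The defect is real and limited. Followed literally, SAP 15.6.2 and the Day 31 carry-over in SAP 10.3 turn about 56% of true stops on Days 5-30 into late events when the stop day is missing. The SAP 6.4 set loses 90-93% of true Day 2 withdrawals with a missing stop day. The start-date part is narrower: it concerns drugs ongoing at surgery, mainly anticoagulants for paroxysmal AF, and year-only later starts.

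The shares rest on evenly spread surgery dates, the stated spread of true dates and exit at Day 367. The total effect cannot be computed, because the documents do not give the frequency of partial dates. Affected are the additional AF-drug variables and win ratio in SAP 10.3, the supplementary set in SAP 6.4 and the prior-medication table. The direction of bias is not fixed. The plan should be changed, but the main primary analysis does not depend on it.

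**What to change.** Keep 15.6.1 and 15.6.2 for the prior/concomitant tables, with two additions:

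1. If a drug is recorded as in use before surgery, impute an incomplete start no later than the day before treatment. State that such a drug is not a new post-surgical event in SAP 10.3.
2. For the AF-drug and win-ratio variables in SAP 10.3 and the set in SAP 6.4, add a sensitivity analysis using the earliest and the latest dates consistent with the known date parts. Apply it to the ongoing status at Day 31 and to the Day 3 and Day 7 beta-blocker criteria. If both ends agree, partial dates do not matter; if not, the report shows by how much.

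An incomplete drug start should not be set to the first recorded AF onset. That derives one outcome from another and is undefined where no AF was recorded.

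The cost is a few sentences in the SAP and a small amount of programming. No new data are needed.

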15.6.2 Incomplete Stop Date

The following rules will be applied to impute the missing numeric fields for an incomplete prior or concomitant medication stop date. If the date of the study exit is missing, the last available study visit date will be used as the study exit date.

Missing month and day

- If the year of the incomplete stop date is the same as the year of the study exit, the month and day of the study exit will be assigned to the missing fields
- If the year of the incomplete stop date is before the year of the study exit, *December 31* will be assigned to the missing fields
- If the year of the incomplete stop date is after the year of the study exit, *January 1* will be assigned to the missing fields

Missing month only

• If only the month is missing, the day will be treated as missing and both the month and the day will be replaced according to the above procedure

Missing day only

- If the month and year of the incomplete stop date are the same as the month and year of the study exit, the day of the study exit will be assigned to the missing day
- If either the year of the incomplete stop date is before the year of the date of the study exit or if both years are the same, but the month of the incomplete stop date is before the month of the date of the study exit, the last day of the month will be assigned to the missing day

• If either the year of the incomplete stop date is after the year of the date of the study exit or if both years are the same, but the month of the incomplete stop date is after the month of the date of the study exit, the first day of the month will be assigned to the missing day

15.7 Character Values of Clinical Laboratory Parameters

If the reported value of a clinical laboratory parameter cannot be used in a statistical summary table because, for example, a character string is reported for a parameter of the numeric type, a coded value must be appropriately determined for use in the statistical analyses. The actual values, however, as reported in the database will be presented in the data listings.

Table 15–2 shows examples of how some possible laboratory results should be coded for the analysis.

Laboratory Test, SI Unit	Possible Laboratory Results	Coded Value for Analysis		
CHEMISTRY				
ALT, U/L	< 5	5		
AST, U/L	< 5	5		
Bilirubin, total, µmol/L	< 2	2		
URINALYSIS		·		
	$= OR > 55, \ge 55, > 0$	Positive		
Glucose, mmol/L	\leq 0, negative	Negative		
ц	$> 8.0, \ge 8.0$	8.0		
рн	≥ 8.5	8.5		
	$= OR > 3.0, \ge 3.0, > 0$	Positive		
Protein	≤ 0	Negative		

 Table 15-2
 Examples of Coding Special Character Values for Clinical Laboratory Parameters

